7.5 Reporting to Hospital Risk Management

Participating investigators will report to their local Risk Management office any participant safety reports, sentinel events or unanticipated problems that require reporting per institutional policy.

7.6 Routine Adverse Event Reporting

Any Adverse Events related to metformin administration that led to dose-reductions or discontinuation of study medication **must** be reported in routine study data submissions to the PI on the toxicity case report forms. **AEs reported through expedited processes (e.g., reported to the IRB, FDA, etc.) must also be reported in routine study data submissions.**

8. PHARMACEUTICAL INFORMATION

A list of the adverse events and potential risks associated with the investigational agent administered in this study can be found in Section 7.1.

8.1 Metformin Hydrochloride

8.1.1 Description

Metformin HCl is a white crystalline powder soluble in water and 95% ethyl alcohol. It is practically insoluble in ether and in chloroform. Melting Point: 218-220

Metformin HCl is a biguanide derivative producing an antihyperglycemic effect which can only be observed in man or in the diabetic animal and only when there is insulin secretion. Metformin, at therapeutic doses, does not cause hypoglycemia when used alone in man or in the non-diabetic animal, except when using a near lethal dose. Metformin has no effects on the pancreatic beta cells. Metformin absorption is relatively slow and may extend over about 6 hours. The drug is excreted in urine at high renal clearance rate of about 450 mL/min. The initial elimination of metformin is rapid with a half-life varying between 1.7 and 3 hours. The terminal elimination phase accounting for about 4 to 5 % of the absorbed dose is slow with a halflife between 9 and 17 hours. Metformin is not metabolized. Its main sites of concentration are the intestinal mucosa and the salivary glands. The plasma concentration at steady-state ranges about 1 to 2 mcg/mL. Patients should be cautioned against excessive alcohol intake, either acute or chronic, when

taking metformin HCl, since alcohol intake potentiates the effect of metformin on lactate metabolism.

8.1.2 Form of Medication

Metformin tablets will be purchased from commercially available source.

8.1.3 Storage and Stability

Metformin HCL should be stored at room temperature (15 to 30C) in well closed containers.

8.1.4 Handling

There are no special requirements for the handling of metformin HCl.

8.1.5 Availability

Metformin or it's corresponding placebo will be provided at no cost to research participants. The drug/placebo combination will be purchased by research pharmacy.

8.1.6 Preparation

Metformin capsules and matched placebo will be prepared at DFCI Research Pharmacy.

Metformin Active Drug capsules: Metformin tablets (500 mg ER) will be encapsulated in empty capsules (opaque, "000" size). The remaining capsule space will be filled by cellulose microcrystalline (NF).

Matched Placebo capsules: The identical empty capsules will be filled with cellulose microcrystalline (NF) to prepare matched placebo capsules.

6-Month Crossover Metformin Active Drug capsules: Patients will receive the metformin tablets (500 mg ER) directly from stock bottles within the DFCI Research Pharmacy.

Active Drug and Matched Placebo capsules look identical in appearance.

8.1.7 Administration

The institutional research pharmacy will dispense ample medication for the duration of the 6-month treatment phase based on the randomization schedule provided by institutional statisticians and the Office of Data Quality.

All subjects will be dispensed and mailed a 3-month supply of the study agent after the baseline visit, once eligibility is confirmed and randomization occurs. The remainder of the medication will be shipped at the end of cycle 3, after a safety assessment is completed. If additional study agent is required because of extended delays in scheduling, it may be shipped to the subject per

local policies. At the end of the 6-month treatment phase at the end of study visit, the unused study agent will be counted for compliance and returned to the study team.

For participants in the optional extended treatment (crossover arm), a 3-month supply of metformin will be dispensed at the 6-month visit or by mail shortly after the visit. The remainder of the medication will be shipped after the next safety assessment is completed (end of extended treatment cycle 9). If additional study agent is required because of extended delays in scheduling, it may be shipped to the subject per local policies.

The study team may give instructions to take pills at approximately the same time of day in conjunction with intake of food and at least eight ounces of water and to keep track of missed doses or lost pills on their study diary.

Participants are to be given the following drug administration instructions:

- Keep capsules in the bottle(s) provided and do not transfer them to any other container. Store at room temperature. Capsules are to be taken whole, and not broken or emptied.
- Please take your medication by mouth at the same time every day per the instructions on the study diary or as directed by instructions on the label of your study drug bottle.
- Your medication should be taken with food and water, preferably in the evening to avoid gastrointestinal side effects. If your dose is more than one capsule, please take all capsules at the same time.
- If you vomit after taking a capsule, do NOT take another dose. Please note any vomiting in the Comments section of the diary on the next page.
- If you miss a dose of study drug, take it as soon as you remember on the same day. If you miss taking study drug for the entire day, take your regular dose the next scheduled day (do NOT take double your regular dose to make up for the missed dose).
- If you miss a full dose (all of your assigned medication capsules), please record “0” for Number Taken on your diary
- If you are taking 500 mg (1 capsule) and accidentally take an extra capsule, skip the following day’s dose and resume your assigned schedule on the third day, and record the extra capsule on your diary.
- If you are taking 1000mg (2 capsules) and accidentally take an extra capsule, resume your assigned schedule the following day and record the extra capsule on your diary
- If you are taking 1500mg (3 capsules) and accidentally take an extra capsule, resume your assigned schedule the following day and record the extra capsule on your diary
- Please bring any unused metformin and all empty containers and diary to your next visit.

8.1.8 Blinding and Unblinding Methods

In the event of a serious adverse event or other circumstance requiring unblinding, the investigator will contact the research pharmacy, who will then unblind the subject to the investigator if necessary. If the treatment blind is broken, the reason and the date should be

recorded and signed by the investigator. Participants will have the option to be unblinded after the primary outcome measures have been collected.

8.1.9 Ordering and dispensing

The active drug or placebo will be dispensed in blinded fashion by research pharmacy based on randomization result. Each bottle will be labeled with a label identifying study specific information, such as protocol number, dosing instructions, and a caution statement indicating that the agent is limited by United States law to investigational use only and the agent should be kept out of reach of children.

For those participants who are unblinded, found to be on Metformin, and wishing to continue taking Metformin after the 6-month primary treatment/outcome period is complete, an unblinded supply of metformin will be provided. Again, each bottle will be labeled with a label identifying study specific information, such as protocol number, dosing instructions, and a caution statement indicating that the agent is limited by United States law to investigational use only and the agent should be kept out of reach of children.

8.1.10 Accountability

The investigator, or a responsible party designated by the investigator, should maintain a careful record of the inventory and disposition of the agent using the NCI Drug Accountability Record Form (DARF) or another comparable drug accountability form. (See the NCI Investigator's Handbook for Procedures for Drug Accountability and Storage.)

It is necessary to maintain a careful record of the inventory and disposition of all study agent using a drug accountability record form. The Investigational Pharmacy at each participating site is required to maintain adequate records of receipt, dispensing and final disposition of study agent. Include on receipt record from whom the agent was received and to whom study agent was shipped, date, quantity and batch or lot number. On dispensing record, note quantities and dates study agent was dispensed to and returned by each participant.

8.1.11 Destruction and Return

At the end of the treatment phase, unused or expired supplies of the study drug should be returned to the research pharmacy and destroyed according to institutional policies after accountability is performed. Destruction will be documented in the Drug Accountability Record Form.

9. STUDY MEASURES

9.1 Screening/Baseline Assessments

After the prospective participant signs the informed consent form, eligibility will be assessed including review of medical history and clinical blood tests. To minimize additional visits to DFCI during the COVID-19 pandemic, all in-person screening assessments as well as any baseline measures that require in-person collection will occur at the time of a scheduled clinical appointment at DFCI.

All clinical blood tests to confirm eligibility will be reviewed by a clinician; any values outside the normal range will be discussed with the patient's primary oncologist. Participants meeting eligibility criteria will be randomized to metformin or its corresponding placebo and ideally will be mailed the medication/placebo no later than 5 business days after randomization occurs unless a later date is requested by the participant. The participant will be instructed to begin taking the study medication upon receipt.

9.1.1 Pregnancy Screening

For women of child-bearing potential, a urine pregnancy test will be collected. A serum pregnancy test can be waived in certain conditions, such as post-hysterectomy. A urine or serum pregnancy test will only be performed as a Screening/Baseline assessment. As noted in Exclusion Criteria 3.2.5, "Women who are pregnant or who are unable or unwilling to use contraception during the study period are excluded from this study because it is a class B agent which is known to cross the placenta rapidly and is unbound in serum." Although maternal use of metformin is generally considered safe during pregnancy and is not associated with any teratogenic effects to a fetus, any woman who becomes pregnant during the study period will be removed from treatment to avoid any unknown harm.

9.2 Final assessments

End of Study primary outcome assessments should ideally be done within 7 days of completing 6 months of treatment, or for those that were not able to complete 6 months of treatment, as close to the 6 month timepoint as possible. At this visit, a study staff member will collect pill bottles in person or by mail (empty and unused), participants will have 6-month research blood draw and clinical labs performed, bone marrow samples collected if being done as part of standard of care procedures, have weight measured and recorded, and be asked to complete the Final Questionnaire. For individuals who agree to continue to take metformin for an additional 6-months after primary outcomes are assessed, these secondary outcomes will ideally be done within 7 days of completing 12-months of treatment, or as close to that timepoint as possible. Similar to the 6-month assessment, a study staff member will collect pill bottles in person or by mail, participants will have a research blood draw and clinical labs performed, and bone marrow core biopsy/aspirate samples collected if being done as part of standard of care procedures. At this time, weight will be measured and recorded.

9.3 Endpoint assessment

Primary endpoints of the trial are serum monoclonal (M-)protein concentrations/light chains from baseline to 6-months. Mass spectrometry will also be performed on all samples in the [name] lab at Dana-Farber Cancer Institute on a machine from The Binding Site. Mass spectrometry is of particular utility given its increased sensitivity for the detection of plasma cell dyscrasias.

Rationale for primary endpoint: Most cancer prevention trials rely on inferences from surrogate endpoints to measure the intervention impact on cancer risk. MGUS and SMM are unique diseases given that (1) malignant plasma cells are already present in the bone marrow, and (2) their presence can be easily measured in the peripheral blood through the use of M-protein measurements. These measures usually bear a direct relationship with overall tumor burden, and thus the serum protein electrophoresis test used to quantify M-protein concentrations is one of the most common clinical tests used to monitor patients with all stages of the disease continuum (MGUS, SMM and MM). Importantly, M-protein concentrations have been repeatedly shown to reduce after treatment with a range of mild and aggressive MM therapies,³⁰⁻³² indicating that serum M-protein levels can serve as a sensitive and measurable marker of tumor response to an intervention.³³

9.4 Correlative Studies

9.4.1 Bone Marrow Aspirate Collection

Collection of bone marrow aspirate specimens for analysis will be obtained at the times of standard of care bone marrow collections. These collections are highly encouraged but are considered optional. As noted per Eligibility Criteria 3.1.1, a new bone marrow biopsy is preferred for plasma cell determination at screening; however, determination of eligibility can be made from the most recent bone marrow biopsy performed if it was within 2 years of enrollment. As such, bone marrow aspirate specimens may not be available from these procedures for correlative studies. Please note that some participants enrolling in this study will already have research orders in place for biobanking protocols (e.g., protocol #14-174). In this case, every effort will be made to coordinate and synergize with existing effort so that the minimum amount of marrow is collected for research participants. Any sample collected on this trial that has not been exhausted for the purposes of the aims detailed in this study will be stored for future use. Specimens will be collected and subsequently processed, analyzed, and stored at Dana-Farber Cancer Institute at the following address for the [name] Lab:

[name] Lab
Dana-Farber Cancer Institute
[REDACTED]

Bone Marrow Specimens Requested (if available):

- 2x10mL Purple Top Tubes (K2EDTA)
 - Tubes types may be substituted if requested by the study team

Timepoints Requested:

- At any time a standard of care marrow biopsy/aspirate is being performed

Specimens should be labeled with the following:

- Subject Initials
- Subject study number (will include protocol number)
- Visit at which sample was drawn
- Date sample drawn (mm/dd/yyyy)
- Time sample drawn (24-hour clock)

9.4.2 Blood Collection

Collection of blood specimens for analysis will be obtained at the times of standard of care blood draws, whenever feasible. Collection will occur at pre-specified study intervals and may be collected more often if additional standard of care draws are scheduled. Any sample collected on this trial that has not been exhausted for the purposes of the aims detailed in this study will be stored for future use. Please note that some participants enrolling in this study will already have research orders in place for biobanking protocols (e.g., protocol #14-174). In this case, every effort will be made to coordinate and synergize with existing effort so that the minimum amount of blood is collected for research participants. Specimens will be collected and subsequently processed, analyzed, and stored at Dana-Farber Cancer Institute at the following address for the [name] Lab:

[name] Lab
Dana-Farber Cancer Institute
[REDACTED]

Blood Specimens Requested:

- 3 x 10ml Purple Top Tubes (K2EDTA)
- 1x 6ml Red Top Tube (no additive)
 - Tubes types may be substituted if requested by the study team

Timepoints Requested:

- Pre-Treatment/Baseline
- Post Treatment/6-month timepoint (ideally within 7 days)

Label all specimens with the following:

- Subject Initials
- Subject study number (will include protocol number)
- Visit at which sample was drawn
- Date sample drawn (mm/dd/yyyy)
- Time sample drawn (24-hour clock)

9.4.3 Sample Collection Table

Sample Time Point	Recipient	Sample Type	Shipping Method	Container ^{1,2}
Baseline/Pre-Treatment	DFCI	Peripheral Blood	Same day delivery to [name] Lab	3x 10mL Purple Top 1x6ml Red Top
		Bone Marrow Aspirate ⁴		2x10mL Purple Top ¹
End of Study (6 month visit)	DFCI	Peripheral Blood	Same day delivery to [name] Lab	3x 10mL Purple Top 1x6ml Red Top
		Bone Marrow Aspirate ⁴		2x10mL Purple Top

¹ Purple Top= K2EDTA Tube; Red Top= No Additive

² Samples at these time points are **voluntary**, and do not exclude patients from treatment

³ Cell Secure tubes or other tube may be used in place of listed tube types where necessary at the request of the [name] Lab

⁴ Bone marrow aspirate/biopsy only collected if being done as part of routine clinical care. These sample collections are highly encouraged, but are **optional**

9.4.4 DNA and RNA sequencing of tumor cells from the bone marrow

The "clonal evolution" model of cancer emerged amid ongoing advances in technology, especially in recent years during which next generation sequencing has provided ever higher resolution pictures of the genetic changes in cancer cells and heterogeneity in tumors where tumor progression proceeds in a branching rather than in a linear manner, leading to substantial clonal diversity and coexistence of wide genetic heterogeneity^{49,50}. The genomic complexity in MM was recently corroborated by massive parallel-sequencing studies displaying the lack of a universal driving mutation³⁵. Recent studies have shown intraclonal heterogeneity that occurs at different stages of MM^{36,37}. Most recently, exome sequencing confirmed that the heterogeneity observed in MM and how it is likely to be an essential feature of clonal evolution and disease progression^{51,52}. Although treatment is very effective in MM patients nowadays; however, new resistant clones may arise in certain patients causing disease relapse and resistance to maintenance treatment. Moreover, the recent advances in RNA sequencing technologies, like single cell RNA(ScRNA) sequencing is now enabling us to better understand the composition and state of the tumor microenvironment including immune cells and stromal cells. ScRNA sequencing coupled with bulk RNA sequencing will allow us to accurately identify expression levels of CD38 and other proteins on both tumor and immune cells at different time points, and how this would affect treatment response and disease course.

Circulating cell-free DNA (cfDNA) and tumor cells (CTCs) are considered emerging and promising approaches to capture the genomic landscape and heterogeneity of the tumor cells in bone marrow, but from blood samples. We published a proof of concept study in Nature Communication on how blood biopsies were good surrogates for the mutational profile in bone marrow. We plan to expand on this by studying serial samples from patients throughout treatment as a tool for detecting minimal residual disease and new mutations that can rise during treatment.

We plan to perform exome sequencing and RNA sequencing studies on tumor cells obtained at the time of screening as well as from subsequent bone marrow biopsy samples to examine clonal heterogeneity, resistant clones at best response and at time of end of study or at disease progression.

The tumor research samples will be collected at the time of scheduled bone marrow biopsies. From these samples, high quality DNA and RNA for both exome sequencing and RNA sequencing of tumor cells will be obtained. In brief, BM aspirates will be obtained after informed consent. The tumor cells will be collected using CD138+ bead selection (over 90% purity based on prior publications)^{35,36}. For samples that have a small fraction of plasma cells, we will use flow sorting for CD138/CD38/CD56 and CD19-ve to obtain a pure malignant plasma cell population based on prior published markers of malignant plasma cells⁵⁵.

WES of tumor and germline DNA

WES will be performed on all samples pre and post-treatment on the clinical trial to study clonal evolution of malignant cells. DNA will be isolated and libraries will be hybridized to Illumina human whole exome capture kit as previously described. All sequencing studies will be performed at the Genomic Platform of the Broad Institute. Samples will be multiplexed and sequenced on Illumina Novaseq to obtain an average depth of coverage of 175x for tumors and 70x for germlines to have enough sensitivity for mutation detection ⁴¹.

9.4.3 WGS of tumor and germline DNA

Considering the emerging importance of structural variants like, jumping translocations involving important oncogenes, Chromothripsis, and Chromoplexy in MM, we will use an innovative approach to study translocations in MM by low pass WGS (12x mean coverage). Libraries will be prepared using new HiseqX technology (Illumina®) which offers long range phased (i.e. barcoded) reads which enable much more accurate structural characterization. Libraries will be sequenced on a HiSeq X Ten sequencer available at the Broad Institute. This will be performed on the same samples of WES.

9.4.4 Targeted deep sequencing:

To be able to analyze small sub-clones, we will design a specific hybrid capture targeted panel of baits to detect the main MM drivers by deep sequencing. This panel includes exons of significantly mutated genes in MM as well as those identified in WES of our samples, baits on the main CNA regions (17p, 1q, 13q) and baits on the IGH, IGL, IGK and MYC loci, enabling us to detect somatic mutations, CNAs and translocations. The total size of the bait set is 2Mb. This will be used for samples at the time of best response and in those samples that do not have enough DNA for WES or WGS. Libraries will be prepared using Agilent's SureSelect XT library prep kit and hybridized to a customized targeted bait set. Samples will be multiplexed and sequenced on Illumina Novaseq with the goal of an average depth of coverage of 1500x to have enough sensitivity for mutation detection at low allelic fraction (1%)41.

9.4.5 Computational analysis and expected outcome.

All bioinformatics and statistical analyses will be performed with guidance of the biostatistics and bioinformatics Core B. Briefly, BAM files aligned to the hg19 human genome will be produced using Illumina sequencing reads and the Picard pipeline⁴². SNVs will be determined using the MuTect2 algorithm⁴³, in single mode for targeted sequencing with additional filters for mutation call such as 1000 genome and COSMIC mutations. Indels and translocations will be determined by the algorithms IndelLocator³⁷ and dRanger, respectively. Focal as well as arm-level copy number variations will be determined based on WES and subsequent application of the GISTIC⁴⁴ algorithm. We will use MutSigCV⁴⁵ to detect candidate cancer genes using three signals of positive selection: (i) increased mutation burden as compared to a background model; (ii) clustering of mutations along the gene; and (iii) enrichment of mutations at likely functional sites. The output of MutSigCV consists of a list of the most significantly genomic events across samples. False-discovery rates (q values) ≤ 0.1 will be considered as significantly mutated. All candidate SNVs/indels/CNVs will be reviewed in the IGV⁴⁶.

9.4.6 RNA sequencing of tumor cells.

For RNA Sequencing, poly-A selection and cDNA synthesis will be performed, followed by library preparation, sequencing (76bp or 101bp paired reads), and sample identification with quality control. Details of experimental design are described in^{62,63-65}. We will perform library construction using a non-strand specific Illumina TruSeq Protocol and sequence coverage to 100M total reads. Analysis will be performed as described in the preliminary data and in previous studies⁶³⁻⁶⁵.

The DNA and or RNA library will be prepared at the [name] Lab, and then sequencing will be done at the following external lab:

Broad Institute Genomics Services
[name]
[name]

Sequencing data will then be provided back to [name] lab in the form of BAM file. The samples that are sent for analysis are exhausted during the process, and thus not able to be returned.

9.4.7 Single-cell sequencing of the tumor microenvironment.

Single-cell RNA sequencing (RNA-seq) of the tumor microenvironment can define genotypic and phenotypic states of tumor cells and surrounding microenvironment, and that the microenvironment affected the gene expression program of tumor cells and their resistance to therapy. We will apply 10X genomics in this study to evaluate the tumor microenvironment and assess specific changes in cell type and transcriptional signature of BM niche cells that correlate with tumor progression or resistance to therapy.

9.4.8 cfDNA and circulating tumor cells (CTCs) from the peripheral blood.

cfDNA sequencing can be challenging because of the small fragment size of DNA in the peripheral blood (average of 166bp), the low yield of DNA and the usual low allelic fraction of tumor-derived DNA among the cfDNA. Therefore, we developed two different approaches to sequence cfDNA. The first approach applies WES and is performed by the Blood Biopsy Group at the Broad Institute. After high-speed centrifugation of frozen samples to eliminate residual cells from plasma, cfDNA was extracted using the Qiagen circulating nucleic acid kit. As little as 5ng of cfDNA was then subjected to library preparation using the Kapa HyperPlus kit, which enables us to prepare libraries from small DNA fragments and minimal DNA yield. CfDNA libraries were initially qualified for further sequencing using ultra-low-pass whole genome sequencing (ULP- WGS). The ULP-WGS is a low-cost approach developed by the Blood Biopsy Group to nominate samples containing sufficient tumor fraction in cfDNA samples for WES. Large numbers of cfDNA libraries were multiplexed and sequenced to an average of 0.1X genome-wide sequencing coverage.

9.4.9 Whole-exome sequencing of cfDNA and CTCs:

These studies will be performed at the Blood Biopsy Group at the Broad Institute in collaboration. As described in the preliminary data, cfDNA and CTCs will be subjected to library preparation using the Kapa HyperPlus kit and initially qualified for WES by ULP-WGS. The ULP-WGS will be used to nominate samples containing sufficient fraction of tumor-derived DNA for WES. Qualified matched samples will be hybridized to the Agilent XT v5 enrichment kit, with additional baits on MYC, IGH, IGL and IGK loci. For both cfDNA and CTCs, the coverage goal will be increased to 200x, which enables us to accurately call mutations even with low allelic fraction samples.

All analyses concerning the ULP-WGS will be performed by the bioinformatics team of the [name] Lab and Blood Biopsy Group at the Broad Institute. WES analyses will be performed through the FireCloud, including MuTect⁴³, IndelLocator³⁷, dRanger, GISTIC2.0⁴⁴ and ABSOLUTE¹⁸ algorithms to evaluate SNVs, Indels, translocations, CNVs and mutated cancer fractions. We will further study the correlation of mutated cancer fractions between matched cfDNA, CTCs and BM tumor cells for each patient to characterize the mutational spectrum in the 3 compartments; thus identify their overlapping landscape as well as their potential specificities. Based on our preliminary data, we expect to identify in cfDNA and CTCs more than 80% of the somatic mutations present in BM.

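### Targeted-panel SNVs are called without the germline sequence the plan generates, so inherited variants missing from the filter databases may be kept as somatic and may look gained or lost

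*Combined protocol and SAP*

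**What the plan says.** Section 1.3 lists the molecular evolution of tumour cells under metformin as a secondary objective. The sequencing plan is in section 9.4, where some subsection numbers repeat, so titles are used here.

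- *DNA and RNA sequencing of tumor cells from the bone marrow*: marrow from screening and later biopsies is sequenced "to examine clonal heterogeneity, resistant clones at best response and at time of end of study or at disease progression". For the exome, "WES will be performed on all samples pre and post-treatment on the clinical trial to study clonal evolution of malignant cells", with an "average depth of coverage of 175x for tumors and 70x for germlines".
- *WGS of tumor and germline DNA*: "low pass WGS (12x mean coverage", and "This will be performed on the same samples of WES".
- *Targeted deep sequencing*: a 2 Mb bait set at 1,500x, aimed at allele fractions down to 1%. It is "used for samples at the time of best response and in those samples that do not have enough DNA for WES or WGS".
- *Computational analysis and expected outcome* (9.4.5): MuTect2 is run "in single mode for targeted sequencing with additional filters for mutation call such as 1000 genome and COSMIC mutations". All candidate calls are then reviewed in IGV.

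No text says that germline reads are used when panel variants are called or when candidates are reviewed.

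**The concern.** A database filter removes only the variants the database lists. An inherited variant private to a person or family passes a population filter, and without a matched normal nothing else in the stated calling step identifies it as inherited.

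This matters because different time points may be read on different assays. Exome sequencing is assigned to samples before and after treatment. The panel is assigned to best-response samples and to samples short of DNA. If exome calls are made against germline, the same inherited variant is removed at one time point and kept at another. On a best-response sample it would resemble a mutation acquired under treatment. On a low-DNA baseline sample it would resemble a clone later lost.

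Low-DNA samples are plausible here. Section 3.1.1 admits MGUS participants with under 10% marrow plasma cells, and section 9.4 already plans flow sorting for samples with few plasma cells.

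**Working it through.** The inputs from section 9.4 are depths of 12x, 70x, 175x and 1,500x, a 2 Mb panel, a 1% target allele fraction, and tumour purity above 90% after selection. Read counts are treated as binomial, X ~ Bin(depth, allele fraction).

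1. **The plan's own sensitivity figure.** At 1,500x and 1%, the expected count is 1,500 × 0.01 = 15 variant reads. P(X ≥ 5) = 0.999 and P(X ≥ 8) = 0.982. At the exome's 175x, P(X ≥ 5) = 0.032. The panel depth is therefore coherent with its stated purpose, and the problem is not depth.

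2. **Where an inherited heterozygous variant sits on the panel.** For Bin(1,500, 0.5), the central 95% range of the allele fraction is 0.475 to 0.525. P(fraction < 0.40) is about 3 × 10⁻¹⁵. In a copy-neutral region it cannot pass for a small sub-clone.

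3. **Where a clonal heterozygous somatic mutation sits.** The expected fraction is purity / 2. At 90% purity this is 0.45, with range 0.425 to 0.475. At 100% it is 0.50, with range 0.475 to 0.525. Across the stated purity, the range moves from just below the inherited range to coinciding with it. Allele fraction alone does not separate the two reliably.

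4. **Exception under copy loss.** The panel carries baits on 17p, 1q and 13q. Take a clonal one-copy deletion at 90% purity and an inherited variant on the lost allele. The fraction is (0.1 × 1) / (0.9 × 1 + 0.1 × 2) = 0.1 / 1.1 = 0.09, which does resemble a small sub-clone.

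5. **What matched germline would do.** The criterion is at least 3 variant reads at a heterozygous site.
   - 70x exome: P(X ≤ 2) = (1 + 70 + 2,415) / 2⁷⁰ ≈ 2 × 10⁻¹⁸, so detection is effectively certain.
   - 12x genome: P(X ≤ 2) = (1 + 12 + 66) / 4,096 = 0.019, so detection is 0.981.

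6. **Visibility in the participant's baseline tumour exome.** At 175x, the 95% range of the fraction is 0.43 to 0.57 and P(X ≥ 5) is about 1. The variant is present in those reads wherever the exome covers the site, so a deliberate look would find it.

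7. **Illustrative count, on assumptions not in the documents.** Assume 0.5 to 1 heterozygous site per kb, with 0.5% to 5% absent from the filters.
   - Inherited sites in the panel: 2,000 kb × 0.5 to 1 = 1,000 to 2,000.
   - Left after filtering: 1,000 × 0.005 = 5, up to 2,000 × 0.05 = 100 per participant.
   - Left after matching: about 0 at 70x. At 12x, 5 × 0.019 ≈ 0.1 up to 100 × 0.019 ≈ 1.9.

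**The case against.** The strongest defence is that the text does not establish the harm.

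- The filters are given as examples in a condensed description, so others may be applied. The plan also does not say whether a COSMIC match keeps a call or removes it. If unlisted variants were dropped, most private inherited variants would go too.
- All candidates are reviewed in IGV, and step 6 shows that the evidence is usually in reads the team already holds.
- The exome is the assay named for clonal evolution before and after treatment, while the panel is meant for small sub-clones and main drivers. No passage compares panel call lists with exome call lists. Matched calling of the exome is itself only implied by sequencing germline at all. A comparison of panel with panel would show an inherited variant at every time point.
- The source of germline DNA is not stated, and germline sequence is not shown to exist for every participant with a panel sample.
- Marrow is optional and taken only at standard-of-care procedures (section 9.4.1), so few samples may be involved.

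These points stand as limits. They make the error possible and conditional, but they do not remove it. The only stated panel method is single mode, no safeguard is said to use germline or baseline reads, and best-response samples are explicitly to be examined for resistant clones.

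A reader might infer that inherited variants will be reported as new clones, or that false calls will match or outnumber true ones. The documents support neither. The first needs a cross-assay comparison that the plan does not describe. The second rests wholly on assumed densities. With an assumed 1 to 5 somatic mutations per Mb, the 2 Mb panel holds 2 to 10 true ones, and 5 false calls against 10 true ones reverses the claim. A flat rate may also understate true mutations on a panel chosen for genes mutated in myeloma.

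**Conclusion.** The point holds in a limited form. The plan commits to tumour-only calling for the panel while generating a better control that it does not apply. Inherited variants missing from the databases may be kept as somatic, usually near 50% allele fraction and indistinguishable there from clonal mutations. They may look gained or lost if panel calls are set against germline-matched exome calls.

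The size cannot be derived from the documents. The 5 to 100 per participant in step 7 is an illustration on assumed inputs, before any IGV review, and should not be cited as an estimate. The conclusion assumes that exome calls use germline and that call lists are compared across assays; both are plausible but unstated. It would be weakened if germline or baseline reads are in fact displayed at review. The M-protein analysis in section 12.2 does not use these calls and is unaffected.

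**What to change.** In section 9.4.5:

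- Call panel variants against the participant's own germline reads wherever these exist and cover the site. Use the exome first, and the low-pass genome for baits outside the exome.
- Keep the database filters as a second step, and state whether a COSMIC match retains or removes a call.
- Where no germline sequence exists or covers the site, flag the call as tumour-only. Check any apparently new or lost variant in that participant's reads from other time points, and leave unresolved variants out of statements on gained or lost mutations.
- State the source of germline DNA and which reads are shown at IGV review.

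The cost is a few sentences, a changed calling option and some added analysis work. Where germline sequence is already planned, no new sample or participant procedure is needed; where it is not, the tumour-only rule applies. The one technical limit is that removal is less complete where only the 12x genome covers a site, with about 2% of heterozygous sites missed on the three-read criterion.
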